## 4.8 Study Drug Administration

Study drug administration data will be listed by subject, including treatment received, dose level (unit), study day, date, and time of administration.

## 4.9 Prior and Concomitant Medications

All prior and concomitant medications will be coded using the World Health Organization Drug Dictionary version 2022 (or higher) and will be listed individually. The frequency and percentage of prior and concomitant medications will be summarized by Anatomical Therapeutic Chemical and Preferred Name. Separate tables will be given for prior and concomitant medications. Prior medications are defined as those taken within 3 months of informed consent for which the end date and time is prior to the date, and time of first study drug administration. Concomitant medications are defined as those with start date and time on or after the date and time of first study drug administration and those with start date and

time prior to the first study drug administration but with end date and time on or after the date and time of first study drug administration.

If medication dates are incomplete and it is not clear whether the medication was concomitant, it will be assumed to be concomitant.

## 4.10 Safety Analysis

Safety analyses will be performed on the safety set.

Safety analyses will include an analysis of all AEs, ECGs, clinical laboratory data and vital sign measurement results and will be presented using descriptive statistics. No formal statistical analysis will be performed.

### 4.10.1 Adverse Events

A Treatment Emergent Adverse Event (TEAE) is any adverse event that commences after the start of administration of study drug.

AEs with unknown start date/time will be assumed to be treatment-emergent unless the end date/time is known to be before the first administration of study drug. Otherwise, missing, or partial dates will be listed as such.

The incidence of TEAEs (after dosing) will be summarized using the safety set. The MedDRA dictionary Version 25.0 (or higher) will be used to classify all AEs reported during the study by SOC and Preferred Term.

A summary of TEAEs including the incidence of subjects who experienced TEAEs (number and percentage of subjects) and incidence of TEAEs (number of events) will be presented for each treatment group, and by population group (i.e., Japanese vs NJNEA) and overall, by maximum intensity (NCI CTCAE Criteria) and by relationship to study drug.

Serious TEAEs, TEAEs leading to withdrawal will be summarized by SOC and Preferred Term for each treatment group and overall, and by relationship to study drug.

Subjects having multiple AEs within a category (e.g., overall, SOC and Preferred Term) will be counted once in that category. In each table, SOC and Preferred Term will be presented in descending order of overall incidence rate (alphabetical order will be used in case of equal rates).

All AEs will be listed.

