Serum ADA and Nabs (immunogenicity)				X ^r														X				X

- a) Procedures will not occur until informed consent is completed. Consent outside of the defined Screening window (D-21 to D-2) is allowed.
- b) Update only.
- c) Serum pregnancy testing is to be performed at Screening, Day -1 and Day 85 for WOCBP. At other visits, a urine pregnancy test is performed. All post-menopausal females will require an FSH serum test at Screening to confirm post-menopausal status.
- d) Study drug will be administered as a single dose on Day 1 via SC injection, according to the randomization schedule.
- e) On Day 1, breakfast will not be served. Lunch will be served after completion of H4 procedures. Dinner and snack will be served after completion of H8 procedures and at H12, respectively. Standard meals will be served at standard unit times from Day 2 to Day 14. On Day 15 (dismissal day), breakfast will be optional.
- f) AEs and concomitant medications will be collected at each visit from the time of consent until the end of study visit, and daily during study residency.
- g) A Holter ECG assessment must be performed at Screening to exclude pre-existing ECG abnormalities.
- h) Continuous 12-lead telemetry will be recorded from at least 1-hour pre-dose to 24 hours post-dose
- i) Vital signs (respiratory rate, tympanic temperature, blood pressure and heart rate) will be measured after at least 5 minutes rest in supine position, according to the timepoints in Table 5.
- j) 12-lead ECGs (triplicate) will be measured after at least 10 minutes rest in supine position, according to the detailed timepoints in Table 5.
- k) Height will be measured at Screening only.
- l) A Full Physical examination will be carried out at Screening and Day 85. Symptom-directed physical examinations will be performed at all other time-points.
- m) Pre-dose on Day 1. Additional unscheduled safety blood samples may be added at the investigator's discretion.
- n) COVID-19 testing will be carried out as per the site's latest COVID-19 Infection Control Guidelines and pre-entry algorithms.
- o) Injection site evaluations will be performed at pre-dose, 30 mins, 1-hour, 4-hour, 12-hour and 24-hour post-dose. Additional examinations may be performed as 'unscheduled' assessments, as required, until resolution of symptoms. Injection site photos will be taken at the same timepoints to monitor any changes.

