8. ADVERSE EVENTS

The collection, evaluation and reporting of AEs/ARs arising from this clinical study will be performed in accordance with:

- detailed guidance on the collection, verification and presentation of AE/AR reports arising from clinical trials on medicinal products for human use ('CT-3') (2011/C 172/01)
- International Conference on Harmonization (ICH) harmonised tripartite guideline on clinical safety data management: 'Definitions and standards for expedited reporting' E2A
- ICH harmonised tripartite guideline on Development Safety Update Report: E2F
- ICH guideline E2F 'Note for guidance on Development Safety Update Reports (DSUR)'.

It is the Investigator's responsibility to document and report all AEs that occur in the clinical study. The period of observation for collection of AEs extends from the signing of the ICF until the final visit. Additionally, spontaneously reported SAEs will be collected until 30 days after the final study visit. SAEs experienced after this 30-day period will only be reported if the Investigator suspects a causal relationship with the study drug.

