8.3 Classification

8.3.1 Assessment of severity

The Investigator will assess the severity of AE/ARs using a categorical grading (mild, moderate or severe) with grading of individual AE/ARs based on global clinical assessment undertaken by an appropriately delegated Research Physician.

Changes in the severity of an AE/AR should be documented to allow an assessment of the AE/AR duration at each level of severity. AE/AR characterized as intermittent require documentation of the start and end of each incidence. Table 16 below guides categorical grading of AE/ARs.

Table 16: Categorical grading of AE/ARs

Grade	Global clinical assessment & application of grading to a diagnosis
Mild	Overall clinical condition is asymptomatic, or symptomatic with all the following characteristics: 
• no or minimal interference with usual social and/or functional activities• no impact, or minimal impact (e.g., of short duration or a return to normal status without intervention), upon usual self-care activities• deviation from reference range for the population and from the participant's clinically determined physiological baseline has no clinical impact and does not signal potential safety concern or unanticipated clinical risk• the condition is reversible to baseline within an anticipated timeframe• intervention or treatment is either not indicated or indicated only to increase participant's sense of wellbeing and comfort, but not due to safety concerns or risk.
Moderate	Overall clinical condition is asymptomatic or is symptomatic with no or minimal impact on usual self-care activities and one or more of the following characteristics: 
• greater than minimal interference with usual social and functional activities• deviation from reference range for the population and from the participant's baseline has clinical impact, but there is no acute safety concern or unanticipated risk. However, should the condition persist and/or occur more frequently, it could signal a potential safety concern or unanticipated risk and should therefore be monitored• reversibility of the condition to baseline condition takes longer than desirable or anticipated, impacting on the participant's wellbeing beyond the mere severity of the condition• further medical assessment, intervention or treatment indicated to increase participant's sense of wellbeing and comfort and to accelerate recovery and/or to prevent worsening.

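### The SAP's TEAE definition has no worsening clause, so a continuous AE that starts before dosing and worsens afterwards can be listed but not tabulated

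*SAP*

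**What the plan says.** SAP 4.10.1 defines a TEAE as "any adverse event that commences after the start of administration of study drug". The protocol uses the term but does not define it, so this is the only definition in the two documents.

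The same SAP section sets the scope of the tables. The main one is "The incidence of TEAEs (after dosing) will be summarized using the safety set", broken down by treatment group, population group, maximum intensity and relationship. Then: "Serious TEAEs, TEAEs leading to withdrawal will be summarized by SOC and Preferred Term for each treatment group and overall". For anything that is not a TEAE the section offers only the statement "All AEs will be listed".

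On collection, protocol section 8 says: "The period of observation for collection of AEs extends from the signing of the ICF until the final visit". Screening opens on Day -21, and a footnote to the Schedule of Assessments (protocol 3.2) adds: "Consent outside of the defined Screening window (D-21 to D-2) is allowed". The pre-dose observation period can therefore be three weeks or longer.

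On recording, protocol 8.3.1 says: "Changes in the severity of an AE/AR should be documented to allow an assessment of the AE/AR duration at each level of severity". For intermittent events it adds that they "require documentation of the start and end of each incidence".

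**The concern.** An onset-only definition classifies an event by when it began, not by what happened to it after dosing. Take a mild AE that begins on Day -1 and becomes severe on Day 3. If it stays one record, its onset is before dosing. Under SAP 4.10.1 it is not a TEAE, whatever its later severity and whatever causality the investigator assigns.

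Comparing safety between Japanese and NJNEA adults is a secondary objective, and SAP 4.10 plans descriptive statistics only, so the tables are the safety result. The scenario is also plausible for this drug. Protocol Table 2 names infection as a theoretical class risk, and section 8.4 makes severe infection an event of special interest. Exclusion 1 covers infections in the four weeks before Screening, not those that begin between Screening and dosing.

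**Working it through.** The plan states no figure that depends on this definition, so there is nothing to reproduce. The check is to follow a post-dose worsening through each way the protocol allows it to be recorded, and then to see whether SAP 4.10.1 tabulates it.

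1. **One continuous AE record with severity changes noted (protocol 8.3.1).** Onset is before dosing, so it is not a TEAE. It is listed only.
2. **New incidence of an intermittent AE (protocol 8.3.1).** It has its own start, after dosing. It is a TEAE and is tabulated.
3. **Worsening entered as an AE in its own right (protocol 8.2).** The AE definition covers worsening of conditions that predate the study. Without any limit on when the disease began, it also covers episodic disease becoming more frequent or intense, recurrence, a new diagnosis, and anything the investigator or sponsor considers an AE. Onset is after dosing, so it is tabulated.
4. **Pre-dose finding recorded as medical history (protocol 7.1).** There is no pre-dose AE record to carry forward. A later worsening can be entered as a new AE with a post-dose start and is then tabulated.
5. **AE with unknown start (SAP 4.10.1).** It is treated as treatment-emergent unless it is known to have ended before dosing.

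Only route 1 loses the event. Protocol 8.3.1 asks for severity changes to be documented but does not say whether worsening opens a new record, so the choice between routes 1 and 3 rests on a convention that neither document states.

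The SAP's handling of neighbouring cases is more inclusive. Route 5 leans towards counting. SAP 4.9 treats a medication that straddles dosing as concomitant. An AE known to straddle dosing and to have worsened is left out of the tables, while a drug given for it is tabulated.

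The weight of one participant, using the planned group sizes (three Japanese groups of 8 and one NJNEA group of 8):

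- treatment group: 1/8 = 12.5 percentage points
- pooled Japanese: 1/24 = 4.2 points
- all participants: 1/32 = 3.1 points

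Participants are counted once per category. These shifts therefore apply only if the participant has no other TEAE in that category. If there is another, the overall incidence does not move, although the preferred-term or maximum-intensity row may.

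**The case against.** The case against has four parts.

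- **The number of events is small.** Inclusion criterion 6a requires no clinically significant illness in the four weeks before dosing, and eligibility is confirmed on Day -1 and again on Day 1. With routes 2 to 4 open, what remains is a minor, continuous event present at dosing that is not held as medical history and worsens without a new entry. This stands. It limits how often the problem can arise, but does not remove it: a minor infection judged not significant could be present at dosing. Nor can 7.1 be relied on to absorb all such events, because it sits uneasily with AE collection from consent.
- **Protocol 10.5 plans a summary of all AEs, and the introduction to SAP 4.10 speaks of analysing all AEs.** This does not close the gap. SAP 4.10.1, which specifies the outputs, tabulates only TEAEs, and SAP 4.15 does not list that narrowing among the deviations from the protocol.
- **Nothing is hidden.** All AEs are listed, 32 participants can be reviewed by eye, and worsening in laboratory values, vital signs and ECGs also shows in change-from-baseline summaries. This stands and keeps the importance low.
- **Severity-change dates may not be available.** The AE items in protocol 8.5 include onset and resolution dates and intensity, but not dates of severity change. However, 8.3.1 requires documentation sufficient to give duration at each level of severity, which implies dating the changes. The data-capture form should be checked.

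A reader might infer that every pre-dose AE that worsens is dropped from every AE summary, or that 8.2 allows worsening to be a new AE only for conditions that predate the study. The documents support neither: 8.2 is broader than that, and routes 2 to 4 lead to the tables.

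**Conclusion.** The gap is real but narrow. As written, SAP 4.10.1 leaves a continuous pre-dose AE that worsens after dosing out of the incidence, maximum-intensity, relatedness and serious-event tables, provided it is kept as a single record. Whether it is kept that way depends on a recording rule that neither document states.

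The documents give no count of such events, and it may be zero. It would be wrong to read 12.5 points as the expected bias: it is the weight of one participant in a group of 8, and only where that participant has no other TEAE in the category. The conclusion assumes the planned group sizes are met and that at least some AEs that begin after consent are recorded as AEs rather than as medical history.

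This is a low-priority clarification in a descriptive study of healthy volunteers, worth making because it is cheap and the groups are small enough for one event to show.

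**What to change.** In SAP 4.10.1:

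- Define a TEAE as an AE that starts, or increases in severity, after the start of study drug administration.
- For a worsened event, tabulate the maximum severity reached after dosing, using the severity changes documented under protocol 8.3.1.
- State whether worsening is kept in the existing record or entered as a new one, and what onset date applies, consistently with protocol 7.1 and 8.3.1.
- Name one grading scale for deciding that severity has increased. The SAP refers to CTCAE criteria for intensity, while protocol 8.3.1 uses mild, moderate and severe.
- Reconcile the TEAE-only tables with protocol 10.5, either by adding a summary of all AEs or by recording the change in SAP 4.15.

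The cost is a clause and a few sentences of text, minor extra programming, and possibly slightly higher reported TEAE counts. If the severity changes are documented as 8.3.1 requires, no new data collection is needed.

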### 4.10.2 Laboratory Data

Biochemistry (including chemistry, serology, FSH, Total IgE, CRP and serum pregnancy results where available), haematology and coagulation will be listed with abnormal parameters being flagged as high (H) or low (L) (where defined) and as being clinically significant or not. Normal ranges, absolute (observed) values and changes from baseline (continuous variables) will also be presented in these listings

## Statistical Analysis Plan

for each parameter and scheduled time point. Clinically significant values for these laboratory parameters will be presented again in a separate listing.

Urinalysis will also be listed with their result, evaluation (normal/abnormal and CS/NCS) and any additional comments, where available.

The quantitative laboratory data for biochemistry, haematology, and coagulation, along with changes from baseline will be summarized using descriptive statistics (n, mean, median, standard deviation, minimum, maximum). Change from baseline values at each assessment will be calculated as the assessment value minus the baseline value. The qualitative urinalysis data and immunogenicity will be summarised and listed.

The number of volunteers presenting out-of-range and clinically significant values will be summarised by treatment group. The scheduled lab value will be used for summary analysis if repeated measurements are made at any time point.

For summary statistics, a lab value with "<" sign will be removed with the numeric value being used. In the listings, the values will be displayed as originally reported by the laboratory.

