Samples and Assessments (safety)	
1. Additional safety assessments may be performed on an individual participant if it is considered clinically necessary by the Investigator for individuals on a case-by-case basis.2. Additional safety assessments (including but not limited to laboratory safety samples, vital signs and ECGs) may be added to the Schedule of Assessments at additional time-points for an upcoming treatment group if necessary from a safety/tolerability perspective, on the basis of evolving data.3. Additional safety assessments may refer to either:
a. an increased number of the same safety assessments planned in the existing Schedule of Assessments.b. additional parameters (specific tests) on assessments already scheduled e.g., troponin tests on safety blood samples.c. additional safety tests requiring additional blood/urine sample collections or other clinical procedures e.g., ultrasound scans.4. Specialist referrals (e.g., to a cardiologist) may be made (and may include all relevant assessments and investigations) if it is considered clinically necessary by the Principal Investigator (PI), Sponsor or Safety Review Committee (SRC) for individuals on a case-by-case basis.5. The timing of safety assessments including but not limited to laboratory safety samples, vital signs and ECGs may be adjusted in accordance with evolving data and dosing schedule.	
I. The maximum blood volume for scheduled assessments is given in Section 7.14. This maximum may only be exceeded if additional unscheduled blood samples/ investigations are performed as necessary to ensure the safety of the individual participants.II. If additional time points for safety assessments are required for upcoming participants in specified treatment groups, this will be documented in a non-substantial amendment, providing the overall risk profile of UPB-101 has not changed.III. If additional safety assessments or parameters are required for upcoming participants in specified treatment groups and have a similar risk profile to those planned in this study protocol, they will be documented in a non-substantial amendment. Additional safety assessments required for upcoming participants in specified treatment groups that are more invasive or have a different risk profile to those in this current protocol must be detailed in a substantial amendment.IV. If there are no clinically significant findings in safety assessments up to Day 85, further follow-up can be discontinued.V. A maximum number of specialist referrals for individuals will be determined on a case-by-case basis and cannot be pre-defined as investigations will be performed as necessary to ensure the safety of the individual participants.

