8.5 Recording of adverse events and follow-up

All (serious and non-serious) adverse events detected by the investigator or spontaneously notified by the participant at each visit/examination must be reported on the appropriate pages of the CRF. The following information should be reported for each adverse event, whether or not it can be attributed to study drug:

- Description of adverse event
- Date of onset/date of resolution
- Characteristics of the event (seriousness, intensity)
- Actions taken (treatment required, or dose adjustments must be reported in the CRF)
- Outcome
- Relationship with study drug (causality assessment) and/or study participation

A clinical laboratory abnormality will be reported as an AE if deemed to be clinically significant by the Investigator. Examples that suggest clinical significance include:

- Accompanied by clinical symptoms
- Leading to a change in treatment with IMP (e.g., dose modification, interruption, permanent discontinuation)

- Requiring a change in concomitant therapy (e.g., addition of, interruption of, discontinuation of, any other change in a concomitant medication, therapy, or treatment)
- The abnormality suggests a disease and/or organ toxicity
- The abnormality is of a degree that requires active management (e.g., discontinuation of IMP, more frequent follow-up assessments, further diagnostic investigation)

All AEs must be followed until the event is either resolved or a satisfactory explanation is found, a new baseline is met, the participant withdraws consent for participation in the study, participant is lost to follow-up, or the investigator considers it medically justifiable to terminate the follow-up. The reason(s) will be recorded in the CRF when the AE follow-up is terminated.

Whenever possible, a diagnosis should be recorded as the AE term rather than a series of symptoms/terms relating to a diagnosis. However, if the diagnosis is unknown, record sign(s) and/or symptom(s). If a diagnosis subsequently becomes available, the diagnosis should be recorded, replacing the original entry(s) where appropriate.

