10.4.5 General considerations

Unless otherwise specified, baseline is defined as the last observed measurement, whether scheduled or unscheduled, prior to the dose of study drug.

Data for repeatedly measured assessments will be analyzed according to the nominal visit, i.e., scheduled assessment. Summaries will be presented by treatment groups with descriptive statistics (number of participants, number of observations [AEs only], mean, standard deviation, median, maximum, and minimum). Categorical variables will be tabulated by frequency and percent of participants per treatment group.

The version of MedDRA and WHODRUG that is current at the time of database soft lock will be used to code the terms for AEs, medical/surgical history and medications.

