10.5 Statistical analysis of safety

All safety analyses will be conducted using the Safety Set.

Individual participant demographics (age, gender and race) and body measurement data (height, weight and BMI) at Screening will be listed. These demographic characteristics and body measurements will be summarized by each treatment group and by each population group (i.e., Japanese vs NJNEA). Other baseline characteristics will be listed only.

AE data will be listed and summarized using descriptive statistics: the number (and %) of participants who had any AEs and the number of AE episodes will be summarized by each treatment group, and by each population group (i.e., Japanese vs NJNEA). All AEs will be summarized and listed by using system organ class (SOC) and preferred term assigned to the event using Medical Dictionary for Regulatory Activities (MedDRA). Furthermore, these events will be summarized by the maximum intensity. The number of participants who had drug-related AEs will also be summarized. Any SAEs and/ or AEs that led to withdrawal will be summarized and listed.

Vital signs data (SBP, DBP, pulse rate, respiratory rate and tympanic temperature) will be listed and summarized, along with changes from baseline, using descriptive statistics (mean, median, standard deviation, minimum, maximum) by each treatment group. Out-of-reference-range values will be flagged as high (H) or low (L) and as being clinically relevant or not: the number of participants presenting out-of-range and clinically relevant values will be summarized.

All safety clinical laboratory data will be listed. Laboratory test results will also be compared to laboratory reference ranges and those values outside of the applicable range will be flagged as high (H) or low (L) and as being clinically relevant or not: the number of participants presenting out-of-range and clinically relevant values will be summarized. The quantitative laboratory data, along with changes from baseline will be summarized using descriptive statistics (mean, median, standard deviation, minimum, maximum). Change from baseline values at each assessment will be calculated as the assessment value minus the baseline value. The qualitative urinalysis data and immunogenicity will be listed only.

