## 4. STATISTICAL ANALYSES

### 4.1 General Notes for Statistical Analyses

In general, descriptive statistics for continuous variables will include number of non-missing values (n), arithmetic mean, standard deviation (SD), median, minimum, and maximum.

Descriptive statistics for PK parameters will include N - the number of participants, n - the number of samples, n(LLOQ) - the number of samples <LLOQ (lower limit of quantification), arithmetic mean, SD - standard deviation, CV - coefficient of variation, geometric mean, median, minimum, maximum.

Categorical variables will be summarized using frequency counts and percentages.

For all tables, except PK parameter tables, descriptive statistics for minimum and maximum will be presented with the same decimal digits as the original data, and with 1 more decimal place than the original data for mean and median; SD will be reported with 2 more decimal places than the original data. Degrees of freedom based on the Kenward Roger approximation will be presented with one decimal (where applicable).

All collected data will be presented in by-subject listings. Listings will be ordered by treatment group and subject number and will include all randomized subjects.

Unless otherwise stated, baseline will be defined as the last non-missing value prior to first administration of study drug. Changes from baseline values will be calculated as the post-baseline assessment value minus the baseline value. If repeated measurements are made at a time point, the first scheduled value will be used for summary analysis, unless otherwise stated in relevant section of this SAP.

Deviations from the planned analyses will be described in the final clinical study report (CSR).

Page layout of the TFLs will be in landscape mode and will be provided as individual RTF format. Further details of page layout will be provided in the TFL shell document.

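### The laboratory abnormality counts may leave out abnormal repeat and unscheduled results, because the SAP's scheduled-value rule follows directly on the count and no any-time count is planned (minor)

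*SAP*

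**What the plan says.** In SAP 4.10.2 (Laboratory Data) two sentences stand next to each other. The first plans the count: "The number of volunteers presenting out-of-range and clinically significant values will be summarised by treatment group". The second gives the rule for repeats: "The scheduled lab value will be used for summary analysis if repeated measurements are made at any time point". Nothing limits the second sentence to by-visit descriptive statistics.

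Two general rules point the same way. SAP 4.1 states "If repeated measurements are made at a time point, the first scheduled value will be used for summary analysis", unless another section says otherwise. Protocol 10.4.5 states "Data for repeatedly measured assessments will be analyzed according to the nominal visit, i.e., scheduled assessment".

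Protocol 10.5 plans the same count with no limit to scheduled values: "the number of participants presenting out-of-range and clinically relevant values will be summarized".

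The protocol expects extra samples. Footnote m to Table 4 says "Additional unscheduled safety blood samples may be added at the investigator's discretion", and Table 6 (section 3.4) says "Additional safety assessments may be performed on an individual participant if it is considered clinically necessary by the Investigator".

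Outside the laboratory tables, protocol 8.5 says "A clinical laboratory abnormality will be reported as an AE if deemed to be clinically significant by the Investigator". SAP 4.10.1 tabulates treatment-emergent events, SAP 4.1 lists all collected data by subject, and SAP 4.10.2 gives clinically significant laboratory values a second listing.

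**The concern.** Taking the scheduled value is a sound convention for a mean at a visit: each participant contributes one value, and repeats drawn for cause do not distort the average. A count of participants who showed an abnormal value asks a different question, namely whether it happened at any time after dosing. Under the scheduled-value convention, a participant whose scheduled result is normal and whose repeat is abnormal is recorded as having no abnormality.

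Protocol 10.4.5 expressly lets an unscheduled value serve as baseline. Neither document says that an unscheduled post-dose value can count as an abnormality. No worst-post-baseline, any-time or shift table is planned that would pick such a value up.

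Comparing safety between Japanese and NJNEA participants is a secondary objective, and SAP 4.10 rules out formal safety testing. The descriptive counts are therefore the results themselves, and in groups of 8 one participant is visible.

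**Working it through.** The documents give no figure to reproduce on this point. The check applies the stated rules to the patterns that can occur at participant level. In each row, all the participant's other post-dose values are normal.

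| Pattern | Under SAP 4.10.2 as written | If any post-dose value counts |
|---|---|---|
| A. Scheduled value abnormal, repeat normal | Counted | Counted |
| B. Scheduled value normal, repeat at the same time point abnormal | Not counted | Counted |
| C. Unscheduled sample between visits abnormal | Not stated; probably not counted | Counted |

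**Pattern A.** The rule does no harm. It keeps the abnormal value and stops a normal repeat from replacing it.

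**Pattern B.** The repeat rule applies directly. The count is a summary, there are repeated measurements at a time point, and the scheduled value is used. SAP 4.1 gives the same answer.

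**Pattern C.** The repeat rule is conditional on several measurements at one time point, so it does not reach a sample with no scheduled counterpart. Protocol 10.4.5, with its analysis by nominal visit, points to leaving such a sample out. Protocol 10.5, with an unrestricted count, leaves room to include it. Two programmers could reasonably build different tables.

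Next, where a value missed under B or C would still appear:

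1. *Judged clinically significant.* Protocol 8.5 makes it an adverse event, and that section draws no line between scheduled and unscheduled samples. If treatment-emergent, it enters the SAP 4.10.1 tables. It also appears in both laboratory listings. The laboratory table could then show 0/8 clinically significant while the TEAE table shows 1/8 for the same finding.
2. *Out of range but not judged clinically significant.* Protocol 8.5 does not require an adverse event, and protocol 8.2 says that an abnormal test needing only a repeat is not necessarily one. The value may then appear in a listing and in no table.

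Scale, by division alone, from the planned group sizes (8 per group, 24 Japanese, 32 in total):

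- one treatment group: 1/8 = 12.5 percentage points
- pooled Japanese participants: 1/24 = 4.2 percentage points
- all participants: 1/32 = 3.1 percentage points

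SAP 4.10.2 plans the count by treatment group, so the first line applies to the planned table. The other two would apply only if pooled columns were added. All three give the weight of one participant; they do not estimate how many would be missed.

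Vital signs: SAP 4.10.3 plans the same kind of count and has no repeat rule of its own, so SAP 4.1 governs and patterns B and C arise there as well.

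**The case against.** The strongest reply is that the rule is narrow and that the safety report has other routes. Much of this stands. A reader might draw three stronger conclusions that the documents do not support.

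- *That abnormal unscheduled results never reach a safety table.* Clinically significant ones do, through protocol 8.5 and SAP 4.10.1.
- *That a dose-limiting laboratory finding could sit only in a listing.* Protocol 4.3 defines an adverse reaction as an adverse event with a reasonable possibility of relationship to the product, and confines the Table 8 rules to treatment-emergent events. A finding that counts under Table 8 is therefore already a related TEAE. Protocol 8.7 also requires potential drug-induced liver injury, as defined there, to be reported as an SAE, and SAP 4.10.1 summarises serious TEAEs separately.
- *That the SAP restricts the counts to scheduled values outright.* It does so for repeats at a time point. For samples between visits it is silent, which is an ambiguity and not a stated exclusion.

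It is also fair to say that no systematic loss of the most informative values has been shown. Where a repeat is drawn to check an abnormal scheduled result, the participant is counted anyway (pattern A).

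The reply does not remove the gap. The adverse-event route does not cover out-of-range values short of clinical significance. Nor does the TEAE table replace a parameter-level count, because protocol 8.5 asks for a diagnosis as the event term where possible.

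**Conclusion.** The point holds in limited form and is minor. As written, the laboratory count omits an abnormal repeat after a normal scheduled value, and it probably omits abnormal results from samples between visits. The loss is confined to out-of-range values not judged clinically significant, plus a possible mismatch between the laboratory table's clinically significant count and the TEAE table. Each affected participant shifts a group's figure by 12.5 percentage points. How many would be affected cannot be derived from the documents and may be none.

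This rests on two readings. The first is that the repeat rule applies to the count it directly follows, which is the natural reading because the rule covers summaries without exception. The second is that analysis by nominal visit extends to the counts; it matters only for samples between visits, and it is less certain.

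**What to change.** In SAP 4.10.2, separate the two uses. By-visit descriptive statistics and changes from baseline keep the scheduled value. For the counts, state that a participant is counted as out of range if at least one post-dose value, scheduled or unscheduled and including repeats, lies outside the reference range. Count clinically significant values separately in the same way. Put the same rule into SAP 4.10.3 for the vital-signs counts, so that SAP 4.1 no longer decides the matter by default.

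The cost is a few sentences in the SAP and some table programming; no extra data are needed. The drawback is that participants with more unscheduled samples have more chances to be counted, which a table footnote can state.

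A shift table of worst post-dose value against baseline status is optional. It would separate new abnormalities from those present before dosing, which can occur because exclusion criterion 9 accepts a participant when two of three bilirubin, ALT or AST results are within the limit.
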